In order to detect a 13% absolute reduction (from 33% to 26%) for the primary outcome of postoperative complications of Clavien-Dindo Grade \geq I up to 30 days after surgery (a risk ratio of 0.8), with 90% power and an overall type I error rate of 5%, a total of 2020 patients (1010 per arm) are required, accounting for 10% drop-out rate.

Randomisation procedure

Randomisation will occur after obtaining informed consent from the eligible patients and shortly before the index surgical procedure is due to start (last-minute randomization). Patients will be centrally allocated to treatment arms in a 1:1 ratio by permuted block randomization stratified with participant centers. To enter a patient into the COIN trial, research staff at each participant site will log on to a secure web-based randomization platform of Redcap data

entry system and obtain a unique patient identification number and allocation assignment. This information will be only revealed to the unblinded investigator who prepare the intervention fluids.

Datasets for Analyses

All statistical analyses within this study will be performed following the intention-to-treat principle. This implies that patients will be analysed in accordance with the treatment groups to which they were initially assigned, as depicted in Figure 1. It is expected that there will be either no or very minimal losses to follow-up for primary and secondary outcomes considering the prospective feature. Patients with missing primary outcome data will be excluded from the analysis (complete-case analysis approach). Missing data for baseline covariates to be included in the analysis model will be accounted for using multiple imputation.

Participation of individual patient in the study will be terminated if they (or their trusted person) withdraw consent. However, if the investigator discontinues the patient's participation, either temporarily or permanently, for reasons in the patient's best interest, especially when serious adverse events are suspected to be related to the intervention, the patient will remain in the analysis to uphold the intention-to-treat principle. Their data will continue to be collected until 30 days after surgery, which marks the final follow-up.

Modified Intent-to-Treat (m-ITT) population excludes individuals who had their

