For all analyses, a significance level of 5% will be used. Multiple comparisons will be conducted without Type I error correction and will be interpreted as exploratory.

Data Presentation and Baseline characteristics

Baseline characteristics will be summarized using descriptive statistics for whole patients cohort and for each treatment group by mean and standard

deviation or median and interquartile range for continuous variables, and the number, frequencies, and percent for categorical variables.

Durations According to Dates

For the indexed surgery, the date of randomization or admission to the intensive care unit corresponding to the surgery date will serve as day 1.

Take, for example, the calculation of the postoperative hospital stay (in days).

The formula is: (Discharge date from hospital - Date of index surgery) + 1

Exact dates will be tracked and documented.

Analysis of the primary endpoints

The primary endpoint, incidence of postoperative complications as defined by higher than grade I Clavien-Dindo classification at 30 days after surgery will be analyzed using Chi-squared test as crude analysis. Unadjusted risk ratios with 95% confidence intervals will be estimated by two-by-two table with the use of log-Normal approximation or other approximation/numeric methods as appropriate. The effect size will be expressed as risk differences (95% confidence intervals) will be estimated using Wald's likelihood ratio approximation test or other methods appropriate, with the number needed to treat as the reciprocal of the risk difference, rounded to the nearest integer.

Secondary Analyses of the primary endpoint

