To account for potential confounders, the adjusted analysis of primary endpoint will use a logistic regression model, where the primary endpoint as the dependent variable and independent variables to include study group (colloid fluid bolus group vs crystalloid fluid bolus group), adjusting for the relevant confounders (planned surgical procedure complexity grade, ASA grade, gender, age, baseline hemoglobin, and baseline creatinine, NPO duration, fluid administration within 12 hours prior to surgery). Odds ratios (95% confidence intervals) will be reported; for those ORs may potentially be biased approximation for RRs, estimates will be obtained via either binomial regressions or converted using bootstrap methods. We will also develop a logistic regression model accounting for the above variables plus any baseline characteristics that appear on visual review to be potentially imbalanced between the study groups.

To account for the center effects, we will fit a mix-effect model with the primary outcome as dependent variable, including group assignment as a fixed effect and participant center (stratification variable) as a random effect. Potential confounders that included in the model are the same as the logistic regression model. Alternative method to use if mixed-effect models fail to reach convergence:

- Include participant sites as a fixed-effect instead of random effect.
- Remove the fixed effect for participant sites
- Adjust for age, hemoglobin, creatinine, fasting duration, etc as a single

continuous variable.

- Remove the covariates in prespecified order to see if convergence reached: gender, hemoglobin, creatinine, age, surgical complexity, ASA grade.

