Prespecified subgroup analyses using formal tests of statistical interaction in a logistic regression model will be performed for the primary outcome to assess whether prespecified baseline variables modify the effect of treatment group on the primary outcome intervention differs among subgroup population. The subgroup analyses will be performed using the same model as for the primary endpoint. Independent variables will include study group assignment, the potential effect modifier of interest, and adding an interaction term between the two, aka the potential effect modifier and the treat arm. The presence of interaction will be tested using a likelihood ratio test comparing the subgroup

analysis model with interaction term, to the primary analysis model without interaction term. The test will be considered significant at the 5% level. A P value for the interaction will be reported. P values less than 0.1 will be considered potential interaction, while values less than 0.05 considered to a confirmed interaction. Non-linearity for continuous variables will be explored and analyzed using smoothed methods such as splines and preferably consider 3-5 knots using a locally weighted regression or partial effects plots.

Patients with complete outcome data will be included in the subgroup analysis. Within each subgroups, we will report summary statistics of the outcome by treatment arm, and a treatment effects and 95% confidence intervals. We will use a forest plot to display the effect of covariates. For presenting the continuous variables, they will be dichotomous for forest plot demonstration.

The pre-specified subgroups are:

- Participant center (1-7)
- age (continuous variable, and < 65 years vs ≥ 65 years)
- gender (male, female)
- BMI (continuous variable, and $< 24 \text{ kg/m}^2$ vs $\geq 24 \text{ kg/m}^2$)
- ASA classification (I, II ,III)
- Surgical procedure (abdominal, reproductive and urogenital system, musculoskeletal and connective tissue, breast & thyroid, facial and orthognathic surgery and ophthalmology, nervous system, other)
- Surgical complexity grade (minor, moderate, major, complex)

- NSQIP any complication risk (continuous variable)
- Inferior Vena Cava Collapsibility Index (continuous variable)
- Baseline SBP (continuous variable)
- NPO duration (continuous variable)
- Fluid administration at 12 hours prior to surgery

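### The subgroup interaction test names the primary analysis model as its comparator; as written, it tests prognosis and interaction together for at least six of the twelve baseline modifiers

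*SAP*

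**What the plan says.** **Full model.** Under Subgroup analyses, the SAP lists the terms of the logistic model: "Independent variables will include study group assignment, the potential effect modifier of interest, and adding an interaction term between the two".

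**Reduced model.** The likelihood ratio test sets the subgroup "analysis model with interaction term, to the primary analysis model without interaction term". The section also says: "The subgroup analyses will be performed using the same model as for the primary endpoint".

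**Decision rule.** "P values less than 0.1 will be considered potential interaction, while values less than 0.05 considered to a confirmed interaction".

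**What the primary analysis is.** Under Analysis of the primary endpoints, the outcome "will be analyzed using Chi-squared test as crude analysis", with an unadjusted risk ratio from the two-by-two table. No covariate enters.

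**Where the adjusted model sits.** The covariate-adjusted logistic model comes under the heading "Secondary Analyses of the primary endpoint". It adjusts for "planned surgical procedure complexity grade, ASA grade, gender, age, baseline hemoglobin, and baseline creatinine, NPO duration, fluid administration within 12 hours prior to surgery".

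**The concern.** A likelihood ratio test of interaction is valid when the two models differ by the interaction term(s) and nothing else. If the reduced model also lacks the modifier's main effect, the test asks whether the modifier predicts complications, or changes the treatment effect, or both. A small P value then cannot be read as evidence of interaction.

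Several listed modifiers may well be prognostic. NSQIP complication risk is constructed to predict complications, and neither candidate comparator contains it. Followed as written, the rule could lead the trial report to describe a purely prognostic variable as a confirmed modifier of the colloid effect. The SAP says that the manuscript will adhere strictly to the plan and that multiple comparisons are not corrected, so nothing later in the plan would catch the error.

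**Working it through.** **1. Which terms does each comparator hold?** The full model is group + modifier + group × modifier.

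| Meaning given to the primary analysis model | Modifier's main effect in the reduced model? | What the test examines |
|---|---|---|
| Crude analysis (group only) | No, for all twelve baseline modifiers | Main effect and interaction jointly |
| Adjusted logistic model | Yes for age, gender, ASA, complexity, NPO duration and prior fluid. No for centre, BMI, surgical procedure, NSQIP risk, vena cava collapsibility index and baseline SBP | Interaction for the first six if the full model carries the same covariates; a joint test for the other six |

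There is a further difficulty with the second row. If the full model holds only the three terms listed in the subgroup section, it lacks haemoglobin, creatinine and the other covariates. The models are then not nested, and the likelihood ratio statistic has no chi-squared reference distribution.

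With the group-only comparator, a continuous or binary modifier gives a test on 2 degrees of freedom instead of 1. Seven centres give 12 (6 main effect + 6 interaction) instead of 6.

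**2. Inputs for the size of the error.**
- Event rates, from Sample Sizes: "In order to detect a 13% absolute reduction (from 33% to 26%) for the primary outcome". The two rates differ by 7 points, not 13; the rates themselves are used here.
- The plan's own figure: the two-proportion formula n = [z₀.₉₇₅√(2p̄q̄) + z₀.₉₀√(p₁q₁ + p₂q₂)]² / (p₁ − p₂)², with p₁ = 0.33, p₂ = 0.26 and p̄ = 0.295, gives (1.264 + 0.824)² / 0.0049 = 890 per arm. Dividing by 0.9 gives 989 per arm, or 1978 in total, which is 2.1% below the stated 2020. The figure reproduces closely enough to use.
- Evaluable patients: 2020 × 0.9 = 1818.
- Treatment effect: 33% against 26.4% (33% × the SAP's risk ratio of 0.8), the same in every subgroup, so there is no true interaction.
- Prognostic strength: **assumption**. The SAP gives none, so a range of odds ratios is shown, per SD for a continuous modifier and between two equal halves for a binary one.

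**3. Simulation.** Each simulated trial was tested with the group-only comparator (2 df) and with the nested comparator (1 df). The table gives the percentage with P < 0.05, from 2000 replicates per row.

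| Modifier | Odds ratio | Group-only comparator | Nested comparator |
|---|---|---|---|
| Continuous | 1.0 | 5.2 | 5.0 |
| | 1.1 | 37.3 | 5.1 |
| | 1.2 | 89.0 | 5.7 |
| | 1.3 | 99.9 | 4.5 |
| | 1.5 | 100 | 5.3 |
| Binary, 50% | 1.0 | 5.2 | 5.3 |
| | 1.1 | 12.6 | 4.9 |
| | 1.2 | 34.0 | 4.3 |
| | 1.3 | 61.1 | 4.9 |
| | 1.5 | 96.2 | 5.5 |

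A second, separate simulation at odds ratios 1.1, 1.2 and 1.5 gave about 34%, 92% and 100% (continuous) and 10%, 35% and 95% (binary), against 4–7% with the nested comparator. At the looser P < 0.1 threshold, the group-only comparator flags a binary modifier in 46.3% of trials at odds ratio 1.2 and 98.2% at 1.5.

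**4. Check by formula.** The joint statistic is approximately non-central chi-squared on 2 df with λ = N·p(1 − p)·Var(M)·(ln OR)². Here p = (0.33 + 0.264)/2 = 0.297 and N·p(1 − p) = 1818 × 0.2088 = 379.6.
- Continuous (variance 1), OR 1.1: λ = 379.6 × 0.00908 = 3.45, rejection 36%.
- Continuous, OR 1.2: λ = 379.6 × 0.03324 = 12.62, rejection 90%.
- Binary (variance 0.25), OR 1.2: λ = 3.15, rejection 34%.
- Binary, OR 1.5: λ = 379.6 × 0.25 × 0.1644 = 15.6, rejection 95%.

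These agree with the simulations.

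**The case against.** The strongest reply is that the ordinary nested test was meant. The paragraph speaks of formal interaction tests, refers to the same model, and contrasts a model that has the interaction term with one that does not. Nowhere does it state that the modifier's main effect is dropped. A chi-squared test is also not a logistic model, so the group-only comparator has to be inferred. This stands as a comment on probable intent. It does not repair the rule, because the text names a specific comparator and never says that it keeps the modifier.

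A second reply is that the adjusted logistic model is the natural candidate and already contains age, gender, ASA and complexity. That is true, and on that reading the problem disappears for six modifiers if the covariates match. It remains for the other six. The separate mixed model does include centre, as a random effect, but it is another secondary analysis and does not help the remaining five.

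A third reply concerns scale. The SAP treats everything beyond the single primary analysis as exploratory, and it will show within-subgroup effects with confidence intervals, so a careful reader could see similar effects beside a small P value. This stands and limits the consequences.

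A reader might infer that any prognostic variable will be declared an effect modifier. The figures do not support that: at an odds ratio of 1.1, a binary factor is flagged in only 10–13% of trials and a continuous one in 34–37%. Nor should a reader infer that the primary result is compromised; this test plays no part in it.

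**Conclusion.** Wrong as written. On either meaning of the primary analysis model, the stated test mixes prognosis with interaction for at least six of the twelve baseline modifiers, and for all twelve on the literal reading. Moderately or strongly prognostic variables would often be reported as effect modifiers when the colloid effect is constant: about 90% of the time for a continuous variable at an odds ratio of 1.2 per SD, and about 95% for a balanced binary variable at 1.5, where about 5% is intended.

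These rates rest on assumed prognostic strengths, the group-only comparator and 1818 evaluable patients. The adjusted-model reading was not simulated, so no rate is claimed for it. The authors may well have intended the nested test. The error is confined to the exploratory subgroup analyses and leaves the primary test and its type I error unchanged.

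**What to change.** Replace the sentence that defines the likelihood ratio test with:

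> *The likelihood ratio test compares the model with group, modifier, their interaction and the covariates with the same model omitting only the interaction term(s); the main effects of group and modifier and all covariates are kept in both models.*

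The section should also state which covariates, if any, the subgroup models carry, so that both models are fully specified. The cost is one or two sentences of SAP text. No data, sample size or primary analysis changes, and the interaction test regains its nominal size.

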In addition, we will perform exploratory analyses for additional effect modifiers that are collected after randomization and have the theoretical potential to be affected by the study group assignment:

- Surgical incision type (open, mini-invasive with endoscopy, endoscopic converted to open)
- Choice of sedatives (etomidate, ketamine, propofol, other).
- Use of vasopressor (yes/no)
- Post-induction hypotension (yes/no)
- SBP after fluid bolus infusion (continuous variable)

Handling of Missing Data

Considering the prospective feature of RCT studies and primary endpoints are short-term outcomes, we anticipate no missing primary outcomes and very rare missing values in other variables if any. All demographics and chronic medical history will be filled on site. Intraoperative data will be monitored and documented during surgeries in the operating rooms. Postoperative follow-ups

will be tracked from the electronic health records until discharge of hospital. Other 30-day follow-up data will be obtained via phone-calls, social media software, or updated medical records from any other medical units where available by trained CRCs. Therefore, missing data will not be imputed for the primary or secondary outcome. In adjusted analyses, missing data for covariates will be imputed by multiple imputation. We will combine estimates of the treatment effect and standard errors from the 10 imputed data sets on the log odds scale using Rubin's rules.

Outliers will be subject to confirmation queries to the investigators. In case of confirmation, no modifications will be made before taken into account during analyses.

Corrections for Multiple Testing

We will conduct a single primary analysis of a single primary outcome. Additional analyses are deemed exploratory and hypothesis-generating. No correction for multiple comparisons will be performed.

Table 1 Clavien-Dindo classification

Grade	Definition
Grade I	Any deviation from the normal postoperative course without the need for pharmacological treatment, or surgical, endoscopic, and radiological interventions.

Grade	Definition
	Allowed therapeutic regimens are: drugs as antiemetics, antipyretics, analgetics, diuretics and electrolytes, and physiotherapy. This grade also includes wound infections opened at the bedside
Grade II	Requiring pharmacological treatment with drugs other than such allowed for grade I complications. Blood transfusions and total parenteral nutrition are also included

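### The SAP labels an uncorrected interaction P below 0.05 as confirmed for each of 12 prespecified modifiers, against its own statement that such analyses are hypothesis-generating

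*SAP*

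**What the plan says.** SAP, Subgroup analyses, tests each modifier by a likelihood ratio comparison of logistic models with and without the interaction term. It gives the level of the test, "The test will be considered significant at the 5% level", and then a graded reading of the result: P below 0.1 counts as potential, and "values less than 0.05 considered to a confirmed interaction".

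The list that opens with "The pre-specified subgroups are" has 12 entries: centre, age, gender, BMI, ASA class, surgical procedure, surgical complexity, NSQIP complication risk, inferior vena cava collapsibility index, baseline SBP, NPO duration, and fluid given in the 12 hours before surgery. Age and BMI are listed in both continuous and cut form. A separate list of five modifiers follows, introduced with "we will perform exploratory analyses for additional effect modifiers that are collected after randomization".

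Two other sections fix the status of such tests. General analysis Principles leaves multiple comparisons uncorrected and has them read as exploratory. Corrections for Multiple Testing reserves confirmatory status for one primary analysis of one primary outcome and adds: "Additional analyses are deemed exploratory and hypothesis-generating. No correction for multiple comparisons will be performed". Neither section exempts the subgroup tests. Scope of the Analysis plan commits the final manuscript to strict adherence to the SAP.

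**The concern.** The subgroup rule gives a verdict that the rest of the SAP withholds. Under Corrections for Multiple Testing, an interaction at P = 0.04 can only generate a hypothesis. Under Subgroup analyses, the same result is confirmed. Because the manuscript is bound to the SAP, authors could cite the plan as authority for the stronger word.

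The modifiers are mostly characteristics known before treatment, such as age, ASA class, baseline SBP and NPO duration. A chance finding reported as confirmed would read as evidence about which patients respond differently to colloid. The temptation to lean on it would be greatest if the primary comparison were neutral.

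**Working it through.** The SAP states no familywise error rate for the interaction tests, so there is no figure of its own to reproduce. The check asks how often the rule, applied as written, would produce a false confirmed interaction.

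**Inputs from the SAP**
- Threshold for the confirmed label: P < 0.05 (Subgroup analyses).
- Number of prespecified modifiers: 12, counted from the list in the same section, one test each.
- Correction: none (General analysis Principles; Corrections for Multiple Testing).

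**Assumptions**
- No true interaction for any modifier.
- Each likelihood ratio test holds its nominal 5% level. This is a large-sample approximation, and it applies to the multi-category modifiers too.
- Dependence between the tests is not given in the SAP, so a range is shown.

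**Step 1: independent tests**
- Expected number of false confirmed labels: 12 × 0.05 = 0.60.
- Chance of at least one: 1 − 0.95^12 = 1 − 0.540 = 0.460, or 46%.

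**Step 2: correlated tests**

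Age, ASA class and NSQIP risk plausibly overlap, as do surgical procedure and complexity. Twelve standard normal test statistics with a common correlation ρ were simulated 400,000 times, and the share of draws with at least one |z| > 1.96 was counted.

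| Assumed ρ | Chance of at least one false confirmed label |
|---|---|
| 0 | 45.9% (agrees with the formula) |
| 0.1 | 45.0% |
| 0.3 | 39.7% |
| 0.5 | 31.9% |

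The values of ρ are assumptions chosen to show the range. The simulation treats every test as a single z statistic, which simplifies the multi-category modifiers.

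**Step 3: comparison**

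Even at ρ = 0.5 the chance is more than six times the 5% that the threshold suggests (31.9 / 5 = 6.4).

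**The case against.** The best defence is that the SAP already limits these results. It says "Additional analyses are deemed exploratory and hypothesis-generating" and repeats the principle in General analysis Principles. On that view the word confirmed is a poor choice in a loosely written sentence and means no more than nominally significant, since the sentence giving the 5% level comes shortly before it. The SAP ties no change of primary conclusion to the label. It also requires subgroup estimates with confidence intervals, interaction P values and a forest plot, so readers would see the full set of tests.

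Much of this stands. The general statements show the intent, and how far a mislabelled subgroup would influence practice is a matter of speculation. But the rule is a two-step scale on which confirmed sits above potential, so it says more than nominal significance. The SAP does not say which text prevails. The general statements contradict the rule; they do not cure it.

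A reader might go further in several ways that the document does not support:

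- **Counting 17 tests, which gives 1 − 0.95^17 = 58%.** This adds the five post-randomisation modifiers. The SAP lists them separately and already calls them exploratory.
- **Taking several modifiers to be tested twice.** Only age and BMI are listed in both forms. The other continuous variables are to be dichotomised for display in the forest plot, which is not stated to be a second test.
- **Objecting equally to the P < 0.1 tier, where 1 − 0.90^12 = 72%.** The word potential is compatible with hypothesis-generating use, so that tier is not part of the contradiction.
- **Demanding a Holm or Bonferroni procedure.** Uncorrected interaction tests are acceptable when they are reported as exploratory, which is the SAP's declared position.
- **Inferring that the primary test's type I error is inflated.** The subgroup tests play no part in the primary analysis.

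**Conclusion.** The point holds as a contradiction within the SAP about what an uncorrected interaction test may claim. With no true interaction, the rule yields at least one false confirmed label among the 12 prespecified modifiers with probability 46% if the tests are independent, and about 32% to 45% for assumed common correlations of 0.5 to 0.1. The exact figure depends on a correlation that the SAP does not give, but it stays far above 5% throughout the range tried. The fault lies in the label, not in the decision to leave the tests uncorrected. The change should be made because it governs what the report may say about subgroups.

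**What to change.** In Subgroup analyses, remove the word confirmed and describe an interaction P below 0.05 as nominally significant and hypothesis-generating. State there that all 12 interaction P values will be reported, whatever their size, together with the subgroup estimates and 95% confidence intervals, and that all of them are exploratory in line with General analysis Principles and Corrections for Multiple Testing. The wording for P below 0.1 may stay.

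The cost is a short edit to the SAP. It needs no new data, no additional analysis and no multiplicity adjustment. The trial gives up only a claim that its other sections already disown.

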Patients who were given intravenous crystalloid boluses before the induction of general anaesthesia did not significantly impact haemodynamic instability [7].

Yet, there are very limited studies and no clear evidence regarding whether preoperative fluid infusion therapy can improve the postoperative prognosis of patients undergoing general anaesthesia. Considering the benefits achieved through preoperative infusion in relation to post-induction hypotension, we thus hypothesize that preoperative fluid infusion can have an impact on

postoperative complications. Additionally, whether the reduction in post-induction hypotension acts as a mediating effect will also be explored.

COIN (Colloid infusion for Optimal outcomes In Non-cardiac surgery(COIN): a randomized controlled trial. Rationale and Design) aims to investigate whether the preoperative colloid infusion before the induction of anesthesia can reduce the postoperative complications of patients planning to undergo non-cardiac surgery with general anaesthesia comparing to crystalloid. The study is a parallel group, blinded, prospective, randomised controlled, multicentre trial with 1 : 1 allocation ratio.

The trial commenced in July 12, 2023 and the estimated timeline for completion of patient accrual was Mar 31, 2025. The participants will be followed until 30 days after surgery. This statistical analysis plan details the pre-planned analyses and statistical considerations for COIN for transparency of data management and analyses procedures. The trial protocol has been submitted to *BMJ Open* (bmjopen-2025-100293).

STUDY OVERVIEW

Ethics and Study Design

The planned study is a parallel group, blinded, randomised, controlled, multi-centre trial conducted at seven tertiary teaching hospitals across China. The study protocol was initially approved by the institutional review board (IRB)

of the coordinating site (Xijing Hospital: KY20232058-F1) followed by institutional IRB approvals from all participating centres. The informed consent will be obtained from patients before enrollment. One interim analysis was planned at 50% information rate (50% enrolled participants) with primary endpoints at 30 days after surgery) with futility stopping rule.

Study Population

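### Three variables the bolus can change (vasopressor use, post-induction hypotension, SBP after the bolus) are analysed as effect modifiers under the baseline-subgroup rules, and the mediation question in the Background has no stated method

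*SAP*

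**What the plan says.** The Subgroup analyses section opens with a baseline aim: "to assess whether prespecified baseline variables modify the effect of treatment group on the primary outcome". It promises outcome summaries by arm, treatment effects and 95% confidence intervals within each subgroup, a forest plot and an interaction test. The reading rule is "P values less than 0.1 will be considered potential interaction, while values less than 0.05 considered to a confirmed interaction".

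After the list of pre-specified subgroups the same section continues: "we will perform exploratory analyses for additional effect modifiers that are collected after randomization", and adds that these variables "have the theoretical potential to be affected by the study group assignment". Five follow. Besides incision type and choice of sedative, they are "Use of vasopressor (yes/no"), "Post-induction hypotension (yes/no") and "SBP after fluid bolus infusion (continuous variable"). No different model, threshold, form of reporting or caution is given for them.

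Two of the three correspond to outcomes of the trial. The Secondary Endpoint section lists hemodynamic instability within 20 minutes of induction first and vasopressor consumption second, and the analysis section treats the former as post-induction hypotension. The Background presents hypotension as a possible route to fewer complications and says "whether the reduction in post-induction hypotension acts as a mediating effect will also be explored". No later section states how.

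**The concern.** An effect modifier should be fixed before treatment, so that within each of its levels the arms are still randomised groups. If the bolus changes the variable, the levels hold different kinds of patient in the two arms. If colloid prevents hypotension in the easier cases, the colloid patients who still become hypotensive are on average a higher-risk group than the crystalloid patients who do. The colloid patients who do not become hypotensive now include some who would have been hypotensive on crystalloid. Both strata are then tilted against colloid.

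There is a second problem that needs no confounding. Holding hypotension fixed removes whatever part of the treatment effect passes through it, and that is the pathway the Background proposes. Hypotension rows in the forest plot could therefore show nothing, or slight harm, in a trial where colloid helps in exactly the way proposed. As written, these rows are also the only planned analysis that sets treatment, hypotension and the primary outcome together, so a reader may take them as the answer to the mediation question. They do not answer it.

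**Working it through.** The plan attaches no figure to these analyses, so there is none to reproduce. The check sets out the algebra and then an illustration.

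**Inputs from the SAP.** Control complication risk 33% and 1010 patients per arm (Sample Sizes); hypotension in 30–40% of patients (Background).

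**Assumptions.** A reduction in hypotension of a quarter to a half. The Background's figure of more than 50% concerns preoperative fluid in general, not colloid against crystalloid. One unmeasured risk factor with the same log-OR per SD on hypotension and on complications, 0.2 to 1.0.

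**Step 1: full mediation, no confounding.** Let h0 and h1 be the hypotension risks on crystalloid and colloid, and pH and pN the complication risks with and without hypotension, the same in both arms.

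- Overall risk difference = (h1 − h0) × (pH − pN), a benefit when h1 < h0 and pH > pN.
- Difference among hypotensive patients = pH − pH = 0.
- Difference among the others = pN − pN = 0.

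The benefit is real overall and absent from both rows.

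**Step 2: add the unmeasured common cause.** Hypotension halved, confounder log-OR 1.0 per SD, control complications about 33%, no direct effect of colloid. Risk differences, colloid minus crystalloid, in percentage points:

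| Control hypotension | Log-odds effect of hypotension on complications | All patients | Hypotensive | Not hypotensive |
|---|---|---|---|---|
| 30% | 0 | +0.01 | +3.34 | +2.33 |
| 30% | 1 | −3.18 | +3.30 | +2.02 |
| 40% | 0 | +0.02 | +4.11 | +2.98 |
| 40% | 1 | −4.06 | +4.05 | +2.49 |

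The mechanism shows in the mean of the risk factor (30%, first row): 0.748 SD on colloid against 0.589 on crystalloid among hypotensive patients, and −0.132 against −0.253 among the others. In both strata the colloid patients carry more risk.

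**Step 3: range at 35% control hypotension.**

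- Halved, log-OR 0.7–1.0, no effect on complications: +1.5 to +3.9 points of false harm across the two strata.
- Halved, log-OR 0.7–1.0, effect wholly through hypotension: true benefit of 3.6 to 7.3 points, yet +1.0 to +3.9 points of harm across the two strata.
- 35% against 26%, log-OR 0.7–1.0, effect wholly through hypotension: true benefit of 1.9 to 3.7 points, yet +0.5 to +1.7 points.
- Halved, log-OR 0.35: bias at most 0.5 points. At 0.2: at most 0.2 points.

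The false harm thus runs from about 0.1 to about 4 points. The loss of the mediated benefit occurs in every scenario.

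**Step 4: how much mediation is plausible.** For the planned drop from 33% to 26% (7 points) to run wholly through halved hypotension, hypotension would have to raise complication risk by 0.07/(0.30 × 0.5) = 0.47, or by 0.07/(0.40 × 0.5) = 0.35. Full mediation of the planned effect is therefore an extreme case. Under partial mediation the rows lose the mediated part only.

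**The case against.** The SAP supplies part of the safeguard itself. It keeps these variables out of the pre-specified subgroups, calls the analyses exploratory and says openly that assignment may affect the variables. The Corrections for Multiple Testing section treats everything beyond the primary analysis as hypothesis-generating. Hypotension and vasopressor consumption are already compared by arm as secondary endpoints. All of this stands, and it limits the severity. It does not remove the defect: an exploratory label speaks to strength of evidence and multiplicity, whereas the difficulty here is bias, which a larger sample would not reduce.

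The size is also open to challenge. The confounder strength is assumed, and the halving of hypotension is borrowed from a statement about a different comparison. At 1010 per arm with hypotension halved, the 95% confidence half-widths were about 8–9 points among hypotensive patients and 3.4–4.8 points among the others, so the bias would sit within the noise. Both strata shift the same way, with a ratio of stratum odds ratios of 1.00–1.03, so this mechanism would rarely produce a false confirmed interaction. These limits stand too. The interaction test is thus not the main danger; the stratum estimates are.

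A reader might infer three stronger things that the document does not support:

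- That the SAP plans no mediation analysis. The Background announces one; what is missing is any method.
- That the rows will certainly show harm. They may, by an amount that depends on assumptions and can be close to zero.
- That the trial's main result is at risk. The primary analysis does not use these variables.

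**Conclusion.** The point holds in a limited form, at minor to moderate severity. Following the plan would give treatment effects within levels of three variables that treatment can change, under rules written for baseline subgroups. Those contrasts do not estimate subgroup effects. That a fully mediated benefit vanishes from both strata follows from the algebra and needs no assumed confounder. The added false harm of about 0.1 to 4 points is illustrative only: it rests on the assumed confounder (log-OR 0.2 to 1.0 per SD) and on hypotension falling from 35% by a quarter to a half. Separately, the mediation question raised in the Background is left without an estimand, model, confounder set or sensitivity analysis.

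**What to change.** Before database lock:

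1. Remove vasopressor use, post-induction hypotension and SBP after the bolus from the effect-modifier analyses, with no stratum treatment effects and no interaction P values. Report all three by arm as outcomes; for the first two this largely exists among the secondary endpoints.
2. Specify the mediation exploration announced in the Background: direct and indirect effects of assignment through post-induction hypotension, allowing treatment–mediator interaction and adjusting for baseline causes of both hypotension and complications. Candidates already named in the SAP are ASA grade, age, baseline SBP, history of hypertension, NPO duration and prior fluid. Include a sensitivity analysis for unmeasured mediator–outcome confounding, because the method assumes there is none. Keep the analysis labelled exploratory. Otherwise, delete the Background statement.
3. For incision type, use the planned approach if it was recorded before randomisation.

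The cost is a change of SAP wording, the loss of three forest-plot rows that could not be interpreted, and a modest amount of analysis if the mediation question is kept. The sample size and primary analysis do not change. The SAP commits the final manuscript to following it strictly, so the change is better made in the plan than left to the write-up.
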